3.6.2.3. Severity of Adverse Events

The Investigator is to classify the severity (intensity) of an AE according to the following definitions:

- Mild – The subject was aware of the signs and symptoms, but the signs and symptoms were easily tolerated and do not interfere with daily activity.
- Moderate – The signs and symptoms were sufficient to restrict, but did not prevent, usual daily activity for the subject. The subject is still able to function.
- Severe – The subject was unable to perform usual daily activity.

The maximum intensity of an AE (mild, moderate, or severe) will be assessed taking into account the possible range of intensity of the symptom(s).

3.6.2.4. Relationship of Adverse Events to Study Treatments

The Investigator is responsible to assess the relationship of an AE to the IP treatment using good clinical judgment and definitions outlined in [Table 5](#).

Table 5: Relationship of AE to Study Drug

| Association | Definition |
|--------------------|--|
| Not related | The AE is clearly explained by another cause not related to the IP administration; the temporal relationship of the AE to IP administration makes a causal relationship unlikely, or, concomitant medication, therapeutics interventions, or underlying condition provide a sufficient explanation for the observed AE |
| Possibly Related | The AE and administration of IP are temporally related, but the AE can be explained equally well by causes other than the IP administration |
| Probably Related | The AE and use of IP are temporally related, and the AE is more likely explained by IP administration than by other causes |
| Definitely Related | The AE and IP administration are related in time, and a direct association can be demonstrated. Concomitant medication, therapeutics interventions, or underlying conditions do not provide a sufficient explanation for the observed AE |

3.6.3. Reporting Adverse Events

Adverse events that occur from the time of informed consent through completion of the last study visit should be reported.

Every attempt should be made to describe the AE in terms of a diagnosis. If a clear diagnosis has been made, individual signs and symptoms will not be recorded unless they represent atypical or extreme manifestations of the diagnosis, in which case they should be reported as separate events. If a clear diagnosis cannot be established, each sign and symptom must be recorded individually.

Any SAEs occurring in a subject receiving study drug must be reported to the Sponsor within 24 hours of the site being informed of the event, even if the event does not appear to be drug-related. The report must be made by sending a completed SAE Report form to the Sponsor. Any pertinent follow-up information should be provided in a similar manner. Contact information is provided in [Section 3.7.1](#).

3.6.4. Adverse Event Follow-up

Any ongoing AE at the time of study completion or withdrawal will be followed until the AE is resolved or the subject is referred to his/her own PMD. The Investigator and the Sponsor will decide if longer follow-up is appropriate on a case-by-case basis. Subjects who experience any clinically significant AE will remain under medical supervision until the Investigator or the Sponsor's Medical Monitor deems the AE to be resolved, stabilized, or no longer serious enough to warrant follow-up.

3.6.5. Pregnancy reporting

Prior to study enrollment, females of childbearing potential must be advised of the importance of avoiding pregnancy during study participation and the potential risk factors for an unintentional pregnancy.

A UPT will be performed on all females of childbearing potential at Day 1 (day of first patch application) and EOS. All women of childbearing potential will receive a UPT prior to the first study drug administration and the study drug must be withheld until the results of laboratory pregnancy testing are available. If pregnancy is confirmed, the subject must not receive any study drug and must not be enrolled in the study.

Pregnancy follow-up should be reported to the IRB within 24 hours of first knowledge on a Pregnancy Report Form. Follow up will describe the outcome of the pregnancy, including any voluntary or spontaneous termination, details of the birth, and the presence or absence of any congenital abnormalities or birth defects.

3.6.6. Expected Adverse Events

Any observed response in the patch test area that can be denoted using the irritation criteria summarized in [Table 3](#) and [Table 4](#) will not be considered an AE.

Tape related reactions will only be recorded as AEs when the subject is discontinued due to tape reaction.

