3.3.3. Interruption or Discontinuation of Treatment

In accordance with legal requirements and ICH-GCP guidelines, every subject has the right to refuse further participation in the study at any time and without providing reasons (see also [Section 5.3](#)). A subject's participation is to be terminated immediately upon his/her request. The Investigator should seek to obtain the reason and record this on the case report form (CRF).

If at the time of refusal, a study product has already been administered, the subject should be advised on follow-up safety investigations. If a subject withdraws from the study, all efforts will be made to complete a final evaluation if possible. Subjects discontinued for having experienced an AE will be followed until the AE is resolved, a reasonable explanation is provided for the event, or the subject is referred to his/her own primary medical doctor (PMD). The specific AE in question will be recorded on the appropriate CRF.

If a subject develops a serious adverse event (SAE), his/her termination from the study will be considered by the Investigator. Similarly, if the subject develops conditions over the course of the study which would have excluded his/her entry in the study according to the safety-related medical exclusion criteria, he/she must be withdrawn immediately.

The subject may be withdrawn from the study at any time at the discretion of the Investigator for medical reasons and/or due to non-adherence to the treatment scheme and other duties stipulated in the study protocol. The reasons are to be documented on the CRF.

In addition, the Sponsor retains the right to end the study at any time if the study cannot be carried out as agreed upon in the protocol. In case of premature termination or suspension of the study, the Sponsor's study manager will promptly inform the Investigator/institutions and regulatory authorities of the termination or suspension and the reason for that. It is the responsibility of the Principal Investigator (PI) to notify the Institutional Review Board (IRB) in the case of premature termination/suspension.

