3.6. Adverse Events

3.6.1. Method of Determining Adverse Events

Safety assessments will include recording AEs reported spontaneously by the subject or collected by the Investigator. Adverse events will be collected during the period from the time of the signature of the informed consent form and first trial-related activity performed until the end of the trial. Adverse events will be recorded at each visit throughout the study on the appropriate CRF. Every attempt should be made to describe the AE in terms of a diagnosis. If a clear diagnosis has been made, individual signs and symptoms will not be recorded unless they represent atypical or extreme manifestations of the diagnosis, in which case they should be reported as separate events.

Subjects should be asked whether, since the time of the last observation or visit, they had any of the following:

- Experience any changes in well-being;
- Used any new medications other than those permitted in the inclusion criteria;
- Changed medication regimens (both prescription and OTC); and/or
- Were admitted to a hospital or had any accidents.

All questions should be of a general nature and should not suggest symptoms.

When an AE is suspected, all relevant evaluations will be carried out and appropriate treatment provided. Additional follow-up will be done as necessary ([Section 3.6.4](#)) and recorded in the subject's source documents, and the results will be provided to the Sponsor.

For AE definitions and reporting requirements refer to [Section 3.6.2](#) and [Section 3.6.3](#).

Note: Any observed response which can be denoted using the irritation criteria summarized in [Table 3](#) and [Table 4](#) will not be considered an AE. Likewise, any tape-related irritation will only be noted as an AE when all patches are discontinued due to tape reaction around all sites (see [Section 3.6.6](#)).

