3.6.2. Adverse Event Definitions

3.6.2.1. Adverse Events

Information about all local and systemic AEs, whether volunteered by the subject, discovered by Investigator questioning, or detected through other means, will be collected and recorded on the AE CRF and followed as appropriate.

An AE is defined as any untoward medical occurrence in a patient or clinical investigation subject administered a pharmaceutical product (or cosmetic product), which does not necessarily have a causal relationship with this treatment. An AE can therefore, be any unfavorable and unintended sign, symptom, or disease temporally associated with the use of a medicinal IP, whether or not considered related to the medicinal IP.

Any AE that is considered related to the IP must be followed by the investigator until it is resolved or until the medical condition of the subject is stable; all relevant follow-up information will be reported to MC2 or designee.

Adverse Events will be coded using the Medical Dictionary for Regulatory Activities (MedDRA). Medical conditions/diseases present before starting study treatment are considered AEs only if they worsen after starting study treatment (any study procedures specified in the protocol). Any AEs occurring before starting study treatment but after signing the ICF are recorded on the Medical History/Current Medical Conditions CRF.

To the extent possible, each AE will also be described by:

1. its duration (start and end dates),
2. the severity grade (mild, moderate, severe),
3. its relationship to the study drug,
4. the action(s) taken, and
5. as relevant, the outcome.

Note: Any observed response which can be denoted using the irritation criteria summarized in [Table 3](#) and [Table 4](#) will not be considered an AE. Likewise, any tape-related irritation will not be noted as an AE.

The outcome of an AE will be classified as recovered, recovered with sequelae, recovering/resolving, ongoing, or death.

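### The blanket exclusion of scored site reactions from AEs has no exception for one that is serious, needs treatment or ends participation (low priority)

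*Protocol*

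**What the plan says.** Section 3.6.6 of the protocol states that "Any observed response in the patch test area that can be denoted using the irritation criteria summarized in" Tables 3 and 4 is not to be counted as an AE. Sections 3.6.1 and 3.6.2.1 carry the same exclusion, there without the restriction to the patch test area. The SAP adds no exception.

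Tape reactions are treated differently, and not consistently:

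- Section 3.6.6: "Tape related reactions will only be recorded as AEs when the subject is discontinued due to tape reaction".
- Section 3.6.1: "any tape-related irritation will only be noted as an AE when all patches are discontinued due to tape reaction around all sites".
- Section 3.6.2.1: "Likewise, any tape-related irritation will not be noted as an AE".

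The follow-up duties are all worded for AEs:

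- Section 3.6.2.1: "Any AE that is considered related to the IP must be followed by the investigator until it is resolved", or the subject's condition is stable.
- Section 3.6.4: "Any ongoing AE at the time of study completion or withdrawal will be followed until the AE is resolved", or the subject is referred to his or her own doctor.
- Section 3.3.3, repeated in 3.3.4: "Subjects discontinued for having experienced an AE will be followed until the AE is resolved", explained, or referred.

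**The concern.** The exclusion is not confined to trivial findings. Table 3 runs up to severe erythema (score 3) and to edema with erosion or vesicles (score 2). Table 4 has notations for epidermal damage and for spread beyond the patch. On Day 2 the study irradiates treated skin with 16 J/cm² of UVA and then 0.5 MED of full-spectrum light, in order to see whether a phototoxic reaction follows. The reaction that the study is built to detect is therefore the one taken out of AE reporting.

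That is sensible for ordinary scores, which are the study's main measurement. It is less sensible for the occasional reaction that is serious, has to be treated, or makes a subject stop. Under 3.6.1 and 3.6.6 a tape reaction that ends participation becomes an AE, while a reaction to the product that does the same does not. At stake are an individual subject's safety oversight and the completeness of the AE tables. The phototoxicity comparison is not at stake.

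**Working it through.** The point does not depend on a calculation. The check traces each duty back to what triggers it and looks for an exception in either document.

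1. **Is the reaction an AE?** Sections 3.6.1, 3.6.2.1 and 3.6.6 all say no if it can be denoted with Table 3 or 4. None has a qualifier for seriousness, treatment or discontinuation.
2. **Can it be an SAE?** Section 3.6.2.2 defines an SAE as an AE that meets one of the listed criteria. A response that is not an AE cannot qualify.
3. **Is it assessed?** Severity (3.6.2.3) and relationship to study drug (3.6.2.4) are rated for AEs. Seriousness is a property of AEs. None of these is required for an excluded reaction.
4. **Is it reported within 24 hours?** Sections 3.6.3, 3.7.1, 3.7.2 and 3.7.3 start from the SAE. The additional triggers are pregnancy (3.7.1, 3.7.2) and, in 3.7.2, death and an unusual frequency of AEs. Excluded reactions do not count towards that frequency.
5. **Is follow-up required?** Sections 3.3.3, 3.3.4, 3.6.2.1 and 3.6.4 start from the AE. The last scheduled reading is at 48 ± 4 hours after irradiation, that is 48 − 4 = 44 to 48 + 4 = 52 hours. Nothing requires contact after that for a scored reaction that is still present.
6. **Does another provision fill the gap?** Three come close:
   - Section 3.3.3 says that, if product has already been given when a subject refuses further participation, "the subject should be advised on follow-up safety investigations". It also asks for a final evaluation where possible.
   - A retest, which waits until the first reaction has cleared, happens only if the investigator decides on one (3.5.1, Retest).
   - Section 3.4.6 allows that the reason for a concomitant therapy may have to be reported as an AE. This is permissive, and it sits awkwardly with the three unconditional exclusions.

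   None of these is a required report or a required follow-up.
7. **Where does the case appear in the output?** No row of Table 14.3.1.1 counts it, including the rows for serious TEAEs and for TEAEs leading to discontinuation. It does appear elsewhere: scores and the phototoxicity assessment in Listing 16.2.6, end-of-study status in Listing 16.2.1 (with the discontinuation reason in Table 14.1.1), and any medication with its indication in Listing 16.2.4.3.
8. **Tape wording.** A tape reaction that leads to discontinuation is an AE under 3.6.6. It is an AE under 3.6.1 if all patches are stopped because of reactions around all sites. It is never an AE under 3.6.2.1.

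**The case against.** The strongest reply is that the serious case hardly exists. Tables 3 and 4 describe erythema, edema, vesicles, superficial erosion, itch, pigment change and similar signs. Ulceration, necrosis, a deep burn, infection, pain and scarring have no symbol there and can still be AEs, and a death is reportable in its own right. What remains is mainly the important-medical-event criterion, and a 2 cm × 2 cm reaction to a single 0.2 g application would seldom meet it. This stands, and it is why the priority is low. It does not answer the cases of treatment or discontinuation, which need no seriousness criterion.

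Discontinuation is also a narrow case. The product is applied once, staff remove the patches after about a day, and only two readings follow. The withdrawal is recorded and tabulated. This stands too.

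Keeping the study's own measurement out of the AE tables is a deliberate choice that avoids double counting. That is right for ordinary reactions, and the proposal leaves it in place.

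Finally, the site is bound by GCP, FDA regulations and its own SOPs, and an investigator might report such a case anyway. This limits the finding to the protocol text. But that investigator would be acting against three explicit statements, and the protocol is the place to settle it.

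**Conclusion.** The gap is real and small. Read as written, the protocol keeps a serious, treated or discontinuing scored reaction outside AE and SAE assessment, reporting and follow-up, and the tape rule contradicts itself across three sections. No size can be calculated, because the documents give no rate for such reactions. With one application per site in screened healthy adults they are probably very rare. The conclusion rests on a literal reading of the text, without sight of the SOPs. Priority is low.

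A reader might infer more than this, in four ways that the documents do not support:

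- *That follow-up to resolution is lost.* AE status would not guarantee it. Depending on the section, follow-up may also end with stabilisation, a reasonable explanation, or referral. What is lost is that set of duties.
- *That any severe reaction escapes a 24-hour report.* Severity and seriousness are separate in 3.6.2.2 and 3.6.2.3. Severity alone would not trigger the report even for an AE.
- *That the case disappears from the record.* It remains in the listings named above. Those are compiled afterwards, however, and do not replace a prompt report.
- *That the phototoxicity result is affected.* The exclusion changes neither the scores nor the ANOVA. Whether a withdrawn subject is analysed depends on the completers rule in SAP 11.2, which is a separate matter.

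**What to change.** Keep the exclusion for ordinary scored reactions. Add one sentence, identical in 3.6.1, 3.6.2.1 and 3.6.6, for example: *A response scored with Table 3 or 4 is also recorded as an AE, and assessed for seriousness, if it meets a criterion in 3.6.2.2, requires medical treatment, or leads to discontinuation.* In the same amendment, give the tape rule the same wording in all three sections. The discontinuation rule in 3.6.6 is the simplest one to adopt.

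The existing follow-up rules (3.3.3, 3.3.4, 3.6.2.1, 3.6.4) and SAE reporting rules (3.6.3, 3.7) then apply without change. A separate follow-up threshold based on scores is not needed, and the documents give no basis for choosing one. Dermal scores, dermal tables and the ANOVA stay as planned.

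The cost is a short protocol amendment, a few reactions that appear in both the dermal and the AE tables, and an occasional follow-up contact after Day 4.

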3.7. Instructions for Rapid Notification of Serious Adverse Events

3.7.1. Safety Contact person and number

Serious adverse events and pregnancies must be reported immediately (i.e., not later than 24 hours after first knowledge). The SAE or pregnancy report should be e-mailed or faxed to United BioSource Corporation (UBC) using the following e-mail or fax-number:

Email: [contact]

[contact]

3.7.2. Reporting Responsibility

Any death, SAE, pregnancy, (see [Section 3.6](#)), or unusual frequency of AEs, must be reported immediately (i.e., not later than 24 hours after first learning of its occurrence) to the Sponsor's study manager by the Investigator, even if the event(s) appear to be unrelated to study treatment. Follow-up information about a previously reported SAE or pregnancy must also be reported to the Sponsor within 24 hours of receiving it. If the SAE has not been previously documented (i.e., is a new occurrence) and it is thought to be related to the IP, the Sponsor may contact the Investigator to obtain further information. If warranted, an investigator alert may be issued to inform all Investigators involved in any study with the same product (or therapy) that this SAE has been reported.

The IRB should also be notified of SAEs or pregnancies and of any follow-up information in writing, as is practical, and depending on local regulations/IRB reporting requirements.

3.7.3. Reporting procedures

For each SAE, the Investigator will complete a SAE Report Form in English and assess the relationship of each SAE to study treatment. The completed form(s) should be sent by e-mail to the Sponsor within 24 hours of first knowledge of the SAE (as outlined in [Section 3.7.1](#) and [Section 3.7.2](#)). The initial SAE should be reported immediately, even if only preliminary information is available. Follow-up information should be sent by the same Investigator, restating the date of the original report. Either a new SAE form is sent (stating that it is a follow-up), or the original one is resent (with the new information highlighted and a new date provided). The follow-up should describe whether the event has resolved or continues, if and how it was treated, whether the blind was broken or not, and whether the patient continued or discontinued study participation. The form confirmation will be retained.

Pregnancy follow-up (as outlined in [Section 3.6.5](#)) should be reported to the IRB within 24 hours of first knowledge on a Pregnancy Report Form. Follow up will describe the outcome of the pregnancy, including any voluntary or spontaneous termination, details of the birth, and the presence or absence of any congenital abnormalities or birth defects.

3.8. Appropriateness of Safety Measurements

The safety assessments in the study are standard safety measures in clinical trials.

4. STATISTICAL METHODS

4.1. General Considerations for Data Analysis

The focus of the statistical analysis will be the comparison with controls of the phototoxic response to the study products. The parameter for phototoxicity will be the mean of Day 3 and 4 scores (sum of erythema and edema).

The statistical analyses described below will be supplemented by a comprehensive SAP which will be finalized before the database is locked. Any changes to the statistical plans will be described and justified in the final report.

All statistical processing will be performed using the SAS® system (version 9.2 or higher). No interim or subgroup analyses are planned.

4.2. Sample Size and Power Considerations

The sample size of 30 evaluable subjects conforms to industry and regulatory standards for determination of irritation when topical application to skin is followed by light exposure.

4.3. Subject Populations for Analysis

All subjects who receive treatment will be evaluable for AEs. The evaluation of phototoxicity potential of the study products will be assessed for all subjects completing the study.

4.3.1. Background and Demographic Characteristics

Descriptive statistics will be used to summarize demographic characteristics (age, gender, Fitzpatrick skin type, and race) and background characteristics for the randomized subject population. Past/coexistent medical history information for all randomized subjects will be presented in a by-subject listing.

4.3.2. Study Product/Visit Compliance

Descriptive statistics will be used to summarize study product compliance for the randomized subject population.

4.4. Prior and Concomitant Medications

Prior and concomitant medication information for all randomized subjects will be presented in a by-subject listing.

4.5. Efficacy Evaluation

This section is not applicable to this study.

